2. STUDY OBJECTIVES

The specific aim of this study is to compare the effectiveness of NIATx-TI (Arm 2) and Product Training (Arm1) in implementing an evidence-based innovation (A-CHESS). Impact will be measured using the RE-AIM framework:⁵³

- Reach or Participation (Primary Outcome): a) percent and representativeness, based on age, gender, and ethnicity by organizational site, and b) A-CHESS use per each counselor, by days of use;
- Effectiveness: retention rates of eligible patients overall

- Adoption: percent and representativeness, based on age, gender, race, ethnicity, and education level of counselors referring and not referring patients to A-CHESS;
- Implementation: a) organizational readiness for, and b) fidelity of A-CHESS implementation; and c) qualitative and d) cost effectiveness analyses to develop a better understanding of the implementation processes for delivering NIATx-TI compared to product training alone; and
- Maintenance: A-CHESS use (e.g., A-CHESS downloads and days of A-CHESS use) during the post-test phase.

The specific aims of the COVID-19 supplemental study are 1) to understand whether using A-CHESS may help patients manage anxiety and loneliness associated with social isolation, physical distancing, and other changes to daily life during the COVID-19 pandemic, and 2) to understand how patients have adapted to changes in treatment modality during the COVID-19 pandemic. Impact will be measured by offering all patients who have ever signed up for an A-CHESS account the chance to complete an online survey (administered through REDCap) as well as the opportunity for a qualitative interview with a member of our research team using a standardized interview guide.

Study Coordination

The UW-Madison Center for Health Enhancement Systems Studies (CHESS) is the coordinating site for this study. The UW study coordinator will oversee all recruitment activities which includes:

- developing organizational site-specific recruitment and data collection processes that meet study objectives;
- training staff on protocol procedures prior to start of recruitment and continuous monitoring to assure compliance with the protocol and human subjects regulation;
- communicating with clinic site staff as needed via conference calls to monitor progress, inform of protocol changes/distribute new version of protocol, and address unanticipated issues or challenges;
- and manage all study data.

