% who download A-CHESS app and frequency of A-CHESS use in days	Gustafson et al. ⁵⁰	A-CHESS Server - Monthly (Ms 11 - 47) IDPH – Monthly (Ms11 - 47)
Adoption		
% Counselor Using A-CHESS	Knight et al. ⁵⁹	Organizational Survey & A-CHESS Logs
Effectiveness		
Retention (Length of Stay)	Simpson et al. ⁶¹	IDPH- Ms 11 - 50
Maintenance		
Finance Resource Availability	Klein ⁶²	Organizational Survey – Ms 12, 30

Measurement	Measure Source	Data Source/Frequency (for Cohort 1)
A-CHESS Implementation Fidelity	Developed for this trial	Staff Survey – Ms 12, 30
Organizational Change Manager (OCM)	Gustafson et al. ⁶³	Staff Survey – Ms 11, 12, 30
Patient COVID-19 Survey		
Patient socio-demographic and descriptive characteristics: age, race/ethnicity, sex, gender, sexual orientation, education, marital status, income, housing, family size, employment status, health insurance	PhenX repository	Patient COVID-19 Survey – once during March 2021
Criminal justice history	Justice Community Opioid Involvement Network	
Alcohol Use Disorder Severity	Saunders et al.; Babor et al.	
Substance Use Disorder Severity	Skinner	
Loneliness	Hays & DiMatteo	
Anxiety	Cella et al.	
Substance use disorder recovery strengths	Vilsant et al.	
COVID-19 risk and protective behaviors and impact on daily living	Adapted from several COVID-19 surveys	

Qualitative Interviews: Qualitative data will be gathered from organizational staff at four points. Qualitative interviews with clinicians and peer recovery support staff will occur during the intervention phase. The goal of the interviews is to gain a better understanding of patterns with app adoption and use. Phone interviews of up to 30 minutes will be conducted with approximately 15 people at various sites. The interviews will be audiotaped (with participant permission), but the staff person's identity will be protected and in no way be linked to results.

Additionally, the study, interviews with staff from a randomly selected site in all organizations will occur at the end of intervention phase and again at the same site at the end of sustainability phase. The intent of the surveys is to gain a retrospective understanding of what occurred during implementation. Phone interviews of up to 30 minutes will be conducted with up to four people in at each site. The interviews will be audiotaped (with staff participant permission), but the staff person's identity will be protected and in no way be linked to results.

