7. MEASUREMENT OF EFFECT

All scales used in this study have good psychometric properties with similar populations. Listed below are the factors to be measured and measurement instruments with references to validation studies.

Descriptive Statistics - Organizational traits such as admission and rural v. urban will be obtained via IDPH data at four points during the study (N-SSATS⁵⁵). Patient traits such as age, gender, ethnicity, and poverty level will also be obtained at four points during the study via IDPH data (TEDS⁵⁶). Counselor traits such as gender, ethnicity, race, and certification or education level will be obtained via the organizational survey.

REACH - The percentage of patients that download the A-CHESS app and frequency of use in days will be obtained monthly during the study via the A-CHESS server and IDPH data.⁵⁰

Adoption - The percentage of counselors using A-CHESS will be assessed via the organizational survey and A-CHESS logs.⁵⁹

Effectiveness - Retention (length of stay) will be assessed using IDPH data.⁶¹

Maintenance - The organizational survey, which will be administered at two points during the study, will assess Financial Resource Availability.⁶² The staff survey will assess A-CHESS Implementation Fidelity (developed for trial) and Organizational Change Manager (OCM)⁶³. The OCM and A-CHESS Implementation Fidelity will be administered at two points during the study.

Patient COVID-19 Surveys – Surveys will assess how A-CHESS use may have lessened the impact of COVID-19 on anxiety and loneliness. We will collect several patient socio-

demographic traits as recommended by NIH, including age, race, self-identified gender, sex at birth, approximate income level, educational attainment, sexual orientation, marital status, housing type, family size, health insurance. We will use several validated measures to assess patients' substance use severity, loneliness, anxiety, and substance use disorder recovery strengths. Where validated measures are not available due to the rapidly emerging COVID-19 situation, we have drawn measures from existing population-based studies recommended by the National Institutes of Health.

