Mediational (and Maintenance) analysis: We will examine the mediating effects of organizational factors of: % of counselors using A-CHESS, organizational readiness (via OCM), financial resource availability (via Klein's inventory), and A-CHESS implementation readiness on A-CHESS use through a causal mediational analysis, using data from end of intervention periods. These factors will be analyzed using mixed-effects models. Through a mediation analysis,^{68,69} we can estimate the direct (A-CHESS use with NIATx TI and Product Training) and indirect effects (Adoption and Implementation factors) of each implementation arm on A-CHESS use. We will test the mediation effect of each potential mediator at each time point as well as across time. The R package 'mediation,' will estimate the causal mediation effects, examine moderated mediation effects, and conduct sensitivity analysis.⁷⁰

Effectiveness analysis: We will compare a retention rates in the 2 different arms using hierarchical linear models, where arm membership is used as the treatment assignment. We will examine the distribution of this outcome measure and will implement an appropriate transformation or nonlinear link function when appropriate (e.g., logistic, Poisson, exponential). Monthly data collection of the Effectiveness as well as Reach (A-CHESS Use) measures, allows for analysis after each stage of NIATx-TI.

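### Retention is measured as length of stay with no rule for stays still open at the extract and no admission cut-off; the stated models would then pull the arm difference toward zero

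*Combined protocol and SAP*

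**What the plan says.** Section 2 gives the outcome as "Effectiveness: retention rates of eligible patients overall", with no time point at which retention is judged. Section 7 says instead "Retention (length of stay) will be assessed using IDPH data", and Table 1 in section 5 also equates retention with length of stay.

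Section 9 returns to rates: "We will compare a retention rates in the 2 different arms using hierarchical linear models". It allows a transformation or a nonlinear link once the distribution has been seen, with logistic, Poisson and exponential as examples. It closes with "Monthly data collection of the Effectiveness as well as Reach (A-CHESS Use) measures, allows for analysis after each stage of NIATx-TI".

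The Iowa Department of Public Health (IDPH) supplies retention data monthly (section 5). Table 1 runs them from month 11 to month 50, in a column headed for Cohort 1. Patients are recruited to the app for 18 + 6 = 24 months per organization (section 3).

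The documents contain no censoring rule, time-to-event model, person-time offset, fixed horizon, admission cut-off or discharged-only rule for retention.

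**The concern.** A rate at a horizon and a length of stay are different quantities and need different models. The plan does not choose between them.

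Length of stay is known only once the patient has left treatment. At any extract some patients are still in treatment, and there are more of them in the arm that keeps patients longer. The section 9 tools, as written, have no place for an unfinished stay. Two obvious ways to proceed are to drop it or to enter the time so far. Both shorten the observed stays, and both do so more in the longer-staying arm.

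Retention is the only Effectiveness measure among the RE-AIM outcomes. A real retention benefit could be under-reported, or missed at an early look. A difference could also seem to grow over time only because stays have had time to finish.

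**Working it through.** **The plan's own figure.** No power or effect size is given for retention. The one power figure concerns A-CHESS use: design effect 1 + (62 − 1) × 0.10 = 7.1; effective n per arm 20 × 62 / 7.1 = 174.6; two-sided power for d = 0.352 at 0.05 is 0.908, against the stated 0.90. It reproduces, but has no bearing on retention.

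**Inputs from the documents.** The admission window for app enrollees is 24 months. With training in months 11–15, recruitment ends near months 35–39, which leaves 50 − 39 = 11 to 50 − 35 = 15 months of run-out if month 50 applies to every cohort; 12 is used below. If all admissions in the retention data count, the window is 50 − 11 = 39 months with no run-out.

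**Assumed inputs.** Stays are exponential, with control means of 3, 4 and 6 months. NIATx-TI stays are 25% longer (3.75, 5 and 7.5), and admissions are even over time.

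**Formulas.** Let m be the mean stay, W the admission window, R the run-out and T = W + R.

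- Share of stays open at the extract: p = (m/W)(e^(−R/m) − e^(−T/m))
- Mean stay with open stays cut at the extract: m(1 − p)
- Time so far in open stays, per admission: h = (m/W)[(R + m)e^(−R/m) − (T + m)e^(−T/m)]
- Mean of completed stays only: [m(1 − p) − h] / (1 − p)

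**Worked case: 6 vs 7.5 months, W = 24, R = 12.** p = 0.0332 and 0.0605. Cut at extract: 5.801 vs 7.046, a difference of 1.245, and 1.245/1.5 = 83%. With h = 0.583 and 1.118, completed stays average 5.397 vs 6.310, a difference of 0.913, and 0.913/1.5 = 61%.

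**Worked case: 3 vs 3.75 months, W = 39, R = 0.** p = 0.077 and 0.096. Cut at extract: 2.769 vs 3.389, and 0.620/0.75 = 83%. Completed stays: 2.750 vs 3.351, and 0.601/0.75 = 80%.

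Share of the true difference recovered (completed stays / cut at extract):

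| Analysis | 3 vs 3.75 | 4 vs 5 | 6 vs 7.5 |
|---|---|---|---|
| Final, admissions stop 12 months before extract | 91% / 98% | 81% / 94% | 61% / 83% |
| Final, admissions count through month 50 | 80% / 83% | 72% / 77% | 57% / 66% |
| Look at 18 months, no run-out | 54% / 63% | 41% / 53% | 24% / 37% |
| Look at 6 months, no run-out | 13% / 24% | 8% / 16% | 4% / 9% |

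**Other stay distributions.** Simulated Weibull stays (shape 0.7, 24-month window, 11 months' run-out) recover less. For 3 vs 3.75 the figures are 0.49/0.75 = 65% and 0.63/0.75 = 84%. For 6 vs 7.5 they are 0.54/1.50 = 36% and 0.94/1.50 = 63%. No simulated case of either handling enlarged the effect.

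**Does calling it a rate remove the problem?** Only with a horizon and full follow-up. Take 3 vs 3.75 months and an illustrative 90-day horizon. The true rates are e^(−3/3) = 0.368 and e^(−3/3.75) = 0.449, a difference of 0.081. At a 6-month look, half of all admissions cannot yet have reached 90 days. Counting everyone to date therefore gives about 0.081 × 0.5 = 0.04. Restricting to patients admitted at least 90 days before the extract gave 0.081 in simulation, so the bias is gone.

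**The case against.** The best defence is that the documents do not say open stays will be dropped or cut. Sections 2 and 9 speak of rates, and section 9 allows a logistic link. A fixed-horizon rate in patients with enough follow-up fits that wording and is unbiased. The Poisson or exponential option, with a person-time offset, could also absorb open stays. This stands: the bias is conditional, and the phrase "using hierarchical linear models, where arm membership is used as the treatment assignment" does not tie the plan to a linear model. But no horizon, follow-up requirement or offset is written, and Table 1 and section 7 point to length of stay.

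A reader might infer that the plan schedules retention analyses after each NIATx-TI stage. It does not. Section 9 says only that monthly data make them possible, and the 6- and 18-month looks above are illustrations. The later steps form a repeating cycle, and only one arm has stages, so the matching control time point is undefined. The low early percentages are therefore not the plan's headline loss.

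The run of data to month 50 does soften the final analysis. It does not settle it, because retention covers eligible patients overall rather than app enrollees only, and no admission cut-off is given.

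The size also depends on the handling. Tabulating mean stay by discharge month, with earlier admissions included, gives 0.63 of a true 0.75 months (84%) at month 18 for 3 vs 3.75.

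It is also tempting to assert that stays begun before product training are included. Sections 4 and 5 describe approaching patients in their first three sessions or appointments, while the section 3 criteria do not restrict to new admissions. The documents leave this open.

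**Conclusion.** The concern holds in conditional form. The outcome has two unreconciled definitions, and the stated models make no provision for open stays or late admissions. If length of stay is analysed with open stays dropped or entered as time so far, the arm difference is biased toward zero.

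At the final analysis the loss runs from slight (98% recovered) to substantial (57% recovered) across the exponential cases in the table. It depends on stay length, on the handling and on when admissions stop. Heavier-tailed stays would lose more, so this range is not an outer bound. Every size here rests on assumed stay lengths and an assumed 25% effect, since the documents give neither.

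The documents do not support the stronger claim that the effect will shrink. Nor does the point touch the primary outcome, Reach, or its power statement. It should be settled before retention is analysed by arm.

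**What to change.** In sections 7 and 9, reconcile rate with length of stay, define when an episode starts and ends, and state which admissions count. Then choose one of two analyses.

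1. **Fixed horizon.** Define retention as the share still in treatment at a stated time after admission. Include patients admitted after the site's product training and at least that long before the extract. Use the logistic mixed model that section 9 already allows.
2. **Time to discharge.** Censor open stays at the extract date and use a clustered semi-parametric or flexible survival model. A simple exponential model is not enough: with Weibull stays it returned ratios of about 1.17–1.25 for a true 1.25. This option needs individual admission and discharge dates. Section 5 mentions both site-level aggregates and de-identified individual records without saying which holds retention, so confirm this with IDPH first.

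Apply the same rule to any by-stage look, with each control organization anchored to the calendar months of its matched partner.

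The cost is a few sentences. Under the first option the most recent admissions are left out of each analysis, and no look is possible until the horizon has passed.

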3. SELECTION OF SUBJECTS

This study will engage SUD organizations, counseling and peer recovery support specialist staff at those organizations, and patients of those organizations.

Organizations: Sixteen SUD organizations in Iowa, with a total of forty sites, have agreed to participate in the project.

Counselors: The site coordinator will invite all outpatient counselors serving adult patients employed by the 16 SUD organizations to be part of the study as part of their role in the participating organizations. Any counselor may formally decline to participate during the training or any time thereafter.

Peer Recovery Support Specialists: Peer Recovery Support Specialists associated with the organization will be invited to be part of the study. Any Peer Recovery Support Specialists may formally decline to participate during training or any time thereafter.

Patients: We will aim to enroll 1,800 outpatients from the 16 enrolled organizations. Each organization is expected to have about 516 A-CHESS-eligible patients on average. We estimate that we will recruit a conservative 30% (or approximately 43 per organizational site) for a total n=1,800 patients in the study. We will recruit patients for the 18-month intervention period plus 6 months into the maintenance period. Patients are eligible for the study if they:

- Are 18+ years old
- Understand English
- Have a SUD diagnosis
- Have access to a smartphone

All patients will be offered the opportunity to complete a survey through REDCap. To date, n=520 patients have created an A-CHESS account. We will also conduct in-depth interviews with 40 patients who have created an A-CHESS account.

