5. TREATMENT PLAN

Treatment as Usual (TAU)/Control: Product Training/On-line Support – SUD organizational sites in the TAU or Control arm will participate in 1. day product implementation (or training) period sessions during Ms 11 - 15. On-line technical support will occur for the 18 months following product training.

Product training consists of two components: A-CHESS Demo and A-CHESS Product Training. During the A-CHESS Demo with the organization's IT, clinical leadership, and the A-CHESS site coordinator, the A-CHESS Product Trainer will:

- a) describe the features of A-CHESS (Tutorial)
- b) provide an A-CHESS organizational case example on how A-CHESS is implemented (including clinical protocols)
- c) provide examples of how to recruit and prepare clinicians and patients for A-CHESS

During the 1-hour A-CHESS Product Training, the organization's A-CHESS Site Coordinator and the A-CHESS Product Trainer will train the counselors and Peer Recovery Support Specialists at each site. Prior to the training, the site coordinator will present the Counselor and Peer Recovery Consent Form to each counselor as well as Peer Recovery Support Specialists and give them the opportunity to consent or decline to participate.

For those counselors that agree to participate, the training will include:

- a) demonstrating A-CHESS features and how A-CHESS allows patients to self-manage their recovery in conjunction with their counselor.
- b) role-playing (or patient simulation) live A-CHESS enrollment with counselors, where they can use the A-CHESS patient description sheet to guide conversations with patients
- c) demonstrating how to use the A-CHESS counselor dashboard.

Following the product training session, on-line technical support will be available. Patients and counselors can call or e-mail questions using the A-CHESS portal.

Counselor and Peer Recovery Support Specialist's role (same for Control and Intervention)

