Use data: A-CHESS use data will be collected monthly to assess the percentage of eligible patients who download the A-CHESS app per month per site and the frequency of use by app user. For the percentage who download A-CHESS, data will be collected during the 18-month intervention period and 6 months of post-intervention period for that organization. Frequency of use data for an individual user will be collected during the 12-month period following initial use of A-CHESS. The app automatically collects use data by placing "cookies" on patients' smartphones (with patients' consent) when they enroll in the study. Data are stored on a central server at CHESS. Electronic data, such as A-CHESS use data, will be stored on a secure DoIT server which is backed up according to a standard protocol. Access to this data will be limited by granting individuals access via their UW user log-in.

The Iowa Department of Public Health (IDPH) will also provide data available through existing IDPH administrative databases. A preliminary analysis of *organizational* data will compare baseline characteristics between the NIATx-TI and Product Training alone organizations, as well as organizations enrolled in the project and eligible organizations not participating (Admissions, Rural v. Urban, and Gender/Age/Ethnicity, and Poverty Level), using the National Survey of Substance Abuse Treatment Services (N-SSATS)⁵⁵ and Treatment Episode Data Set (TEDS)⁵⁶ data definitions.

During the study, IDPH will provide *patient* demographic data (gender, age, and ethnicity, using TEDS definitions) for all patients by organizational site. As part of the organizational survey, we will include questions about *counselors'* gender, ethnicity, and race.

Retention data will be collected by IDPH and provided monthly using existing data.

We will use UW Box to store data received from IDPH.

Supplemental COVID-19 Study – Patient Surveys and In-Depth Interviews

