The Organizational Change Manager (OCM), and ACHESS Implementation Fidelity will be assessed by staff survey at months 11 – 14 and 30 – 33 for the four cohorts. Each survey cycle, at months listed above , will include 280 people per cycle. The 280 staff will include up to 7 participants from the 40 sites and will likely include a supervisor, a member of administrative staff, and up to 5 counselors and Peer Recovery Support Specialists. Since many of the same staff will likely complete surveys in successive cycles, 350 unique staff are expected for survey completion across all cycles. The total is not 560 unique people (e.g., 280 x 2 rounds of surveys) because many of the same people are expected to complete the survey in successive rounds. The 350 unique people projected assumes 25% or 70 new people per round during rounds that occur post-intervention. Hence, there will be 280 unique people in the early intervention – and 70 new or unique people in the subsequent round (post-intervention), for a total of 350.

During the intervention as well as at the end of the intervention phase and at the end of the sustainability phase we will conduct qualitative interviews. We will conduct an interview with staff at an organizational site from each of the 16 organizations in the study. During the intervention we will interview approximately 15 clinicians or peer recovery support staff regarding success with getting patients on the app. We will assess the implementation process in both the product training alone (Arm 1) and NIATx-TI sites (Arm 2).

Staff participation will be voluntary. [name], [name], and a staff person from the Iowa Consortium for Substance Abuse Research and Evaluation will conduct telephone interviews

with up to 4 staff members (the organization's Executive Director, the site's clinical director, the A-CHESS site coordinator at each clinic, and a randomly selected counselor) at 16 sites. This will result in 64 interviews per period for a total of 80 interviews (assuming 25% turnover for between the rounds of interviews). During the interviews, participants will reflect on their participation, issues that arose in using NIATx-TI and A-CHESS, factors that influenced acceptance, and perceptions of short- and long-term effects, as well as unintended consequences.

The grand total of staff surveys for the main study, at n=350, and staff interviews, at n=80 participants, is 430.

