We will create and distribute an information sheet for staff giving them the option to decline to participate in the trial or A-CHESS distribution.

Organizational Data: We will assess Financial Resource Availability Inventory, A-CHESS Implementation Fidelity, and List of Counselors (for counselor A-CHESS participation rates) at two points during the study - at organizational baseline (M 11 - 14) and end of the intervention period (M30 - 33) (M=months are in a range due to the 4 study periods) The Iowa Department of Public Health (IDPH) will provide, by site, aggregate data on Admissions, and Rural v. Urban. This data will be collected from IDPH databases at months 11, 22, 34, and 42

Consumer level: Eligible consumers will be identified in real time during their first three outpatient appointments with a participating SUD treatment site. Site counselors will provide information about the study. If the patient is interested in the study, the counselor will provide a brief introduction to A-CHESS and provide information to the client with the URL to download A-CHESS. If the patient chooses to participate, informed consent will be documented via an IRB-approved consent form on the A-CHESS app.

To be eligible for A-CHESS, SUD consumers must: 1) be >18 years old; 2) understand and agree to an English language consent form via the A-CHESS app; 3) have access to a mobile smartphone, and 4) have an SUD diagnosis.

We anticipate enrolling consumers to use A-CHESS (approximately 43 per organizational per site, for a n=1,800 for the study). The state (IDPH) will provide de-identified data including gender, age, ethnicity, poverty level, and units of service for each site.

During approximately March 2021, all patients who have signed up for an A-CHESS account (to-date n=520) will be invited to participate in a one-time, online, self-report survey through REDCap.

Sources of Materials

All data will be coded before reaching evaluation staff. These include data collected by A-CHESS App server on A-CHESS use as well as organization and staff interview and qualitative survey data. Coding of consumer and counselor/staff data will take place, where necessary, by replacing identifying information (such as consumer and staff names) with code numbers prior to data analysis. A unique study ID number will be assigned to all patient surveys and in-depth interviews. Names collected through the informed consent process will be stored separately.

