Qualitative Analysis: The qualitative portion of the study will support the specific aims by exploring how NIATx-TI and product training are implemented, how implementation affects A-CHESS use, and how staff users react to NIATx-TI, product training, and A-CHESS. *During the study*, interviews with a randomly selected site in all organizations $n=16$ will occur at Ms 26-30 (at the end of intervention phase) and 44-48 (at the end of sustainability phase), with the same sites in each phase, to gain a retrospective understanding of what occurred during implementation. The interviews will include closed and open-ended questions designed to explore participants' experiences within each arm and the perceived effectiveness of each approach in assisting with implementing A-CHESS. The closed-ended questions will be based on elements of CFIR, developed by Damschroder et al. (2013),⁷¹ that will address: 1) intervention characteristics; 2) outer setting; 3) inner setting; and 4) process. The additional open-ended questions will allow for discovery of other factors affecting NIATx-TI, product training, and A-CHESS implementation. The information collected will inform our understanding

of implementation assets, barriers, and potential revisions for each approach. Interviews of up to 30 minutes will be conducted with the organization's Executive Director, the site's clinical director, the A-CHESS site coordinator, and a randomly selected full-time site counselor. Four interviews/organization will result in n=64 interviews per phase and up to n=80 interviews overall (assuming 25% turnover between phases).

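### The end-of-intervention staff interviews are dated months 26-30, before the stated end of the intervention (months 30-33) for three of the four cohorts; the date for the second round also needs a defined phase end

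*Combined protocol and SAP*

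**What the plan says.** Section 9, Qualitative Analysis, plans interviews at one randomly selected site in each of the 16 organizations, with the same sites seen twice: "Ms 26-30 (at the end of intervention phase) and 44-48 (at the end of sustainability phase". The stated purpose is to look back on how implementation went. Section 5 (Qualitative Interviews, and Study Design, Staff level) ties the same two rounds to the ends of the phases without giving months. It also plans a separate set of about 15 interviews while the intervention is running.

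Section 5 dates the end of the intervention in several places:

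- Organizational Data puts the second assessment at the "end of the intervention period (M30 - 33").
- Staff level puts the staff surveys at "months 11 – 14 and 30 – 33 for the four cohorts".
- Table 1, whose months are for cohort 1, has "Organizational Survey – Ms 12, 30".
- The control-arm description has training "sessions during Ms 11 - 15", and then: "On-line technical support will occur for the 18 months following product training".

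On the period after the intervention, Section 3 says: "We will recruit patients for the 18-month intervention period plus 6 months into the maintenance period". For the download percentage, Section 5 (Use data) says "data will be collected during the 18-month intervention period and 6 months of post-intervention period for that organization". Table 1 lists Reach data monthly for months 11-47 and retention data for months 11-50. Section 8 gives the treatment arm 36 months of access to NIATx-TI.

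**The concern.** The two sets of months for the end of the intervention cannot both be right for all four cohorts. A single window of months 26-30 is applied to all 16 organizations, although their starts are staggered and the surveys that close the intervention run over months 30-33.

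The first round is meant to look back on a completed intervention, and the plan already has other interviews for the period while it is running. If most organizations are seen before they finish, the round becomes a second mid-intervention round for them. In the NIATx-TI arm it could miss the late change cycles and Step 7, on sustaining changes. The missed stretch would differ by cohort, which complicates the cross-organization comparisons planned in Section 9. The interviews would also describe an earlier point than the end-of-intervention surveys that feed the mediation analysis.

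**Working it through.** This is calendar arithmetic; no power or error-rate formula applies.

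**Inputs.** Interview windows 26-30 and 44-48 (Section 9). End of intervention 30-33 (Section 5, Organizational Data and Staff level). Training 11-15 followed by 18 months (Section 5, control arm). Cohort 1 surveys at months 12 and 30 (Table 1). Four cohorts of 4 organizations (Section 5, Data collection).

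**Can months 26-30 be reproduced as the end of the intervention?**

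- Training plus 18: 11 + 18 = 29 to 15 + 18 = 33, so 29-33.
- Cohort 1: 12 + 18 = 30, which agrees with Table 1.
- Working back: 26 - 18 = 8 to 30 - 18 = 12. An end at 26-30 needs a start at months 8-12, mostly before training begins at month 11.

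No stated start gives 26-30. It shares only month 30 with the stated 30-33, and only months 29-30 with the derived 29-33.

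**How early would round 1 be?** Assume a one-month stagger, so the cohorts end at months 30, 31, 32 and 33. The lead runs from (end - 30) to (end - 26).

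| Cohort | End | Months before the end |
|---|---|---|
| 1 | 30 | 0 to 4 |
| 2 | 31 | 1 to 5 |
| 3 | 32 | 2 to 6 |
| 4 | 33 | 3 to 7 |

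For cohorts 2-4 the window closes before the intervention ends: 3 × 4 = 12 of 16 organizations. At the extreme, a cohort 4 organization seen at month 26 has had 18 - 7 = 11 of its 18 months.

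**Sensitivity.** If the 18 months are counted from the first survey months (11-14), the cohorts end at 29, 30, 31 and 32. The window then closes too soon for cohorts 3 and 4 only, 2 × 4 = 8 of 16 organizations, by 1-5 and 2-6 months. The conflict is smaller on that count but remains.

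**Round 2.** The end of the sustainability phase depends on which figure is taken as its length:

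| Reading | Phase end | Months 44-48 relative to it |
|---|---|---|
| 6 months after 30-33 | 36-39 | 44 - 39 = 5 to 48 - 36 = 12 months late |
| 36 months from starts at 11-14 | 47-50 | reaches the end for cohorts 1-2; 1 to 6 months early for cohorts 3-4 |
| 18 months after 30-33 | 48-51 | reaches the end for cohort 1; 1 to 7 months early for cohorts 2-4 |

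The second window is exactly the first plus 18 (26 + 18 = 44, 30 + 18 = 48). Section 9 therefore seems to run on a timeline that starts earlier than the one in Section 5.

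**The case against.** The strongest reply is that Section 5 already schedules both rounds by phase end, so the governing rule is sound and only the months in Section 9 are off. Cohort 1 finishes inside the window. The 7-month figure needs the last cohort to be seen in the first month of the window, which the text does not say. Figure 2, the cohort timeline, is not reproduced and may define the phases. All of this is fair. It limits the point to a date conflict and makes the 7 months an upper bound. It does not remove the conflict, because no timeline can make both 26-30 and 30-33 the end of the intervention for all cohorts.

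A reader might go further and infer that round 2 also misses its mark, coming 5-12 months after a sustainability phase that ended at months 36-39. The documents do not support this. Months 36-39 appear nowhere in them. The 6 months are a recruitment window and a download-data window, and recruiting for 6 months into the maintenance period suggests that the period continues afterwards. The 36 months of access and the data collection to months 47 and 50 fit an end near months 47-50. The month-47 figure is not decisive by itself: 11 + 24 months of recruitment + 12 months of individual use data = 47, which also fits a 6-month post-intervention window. The length of the phase is thus open on the text available.

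Nor does it follow that round 2 covers a period without data. Table 1 carries the Reach series to month 47 for cohort 1, and a patient enrolled at months 36-39 contributes use data to months 48-51.

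A reader might also fear that early interviews prompt barrier-solving in control sites while Reach is still being measured. That is speculative. The plan already interviews staff during the intervention, and nothing suggests that an interview of up to 30 minutes acts like change-team training and monthly coaching.

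**Conclusion.** Round 1 is wrong as written. Its window reaches the stated end of the intervention only for cohort 1. On the stated months 30-33 and a one-month stagger, 12 of 16 organizations would be interviewed 1 to 7 months early, the exact lead depending on the cohort and on when in the window it is seen. Counting from the first survey months instead, it is 8 of 16.

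For round 2 the finding is narrower: the text supports more than one end for the sustainability phase, and months 44-48 do not reach that end in every cohort on any of the three readings tried. It is not established that the round comes too late.

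The consequence is confined to a secondary qualitative component; primary Reach, power and error rates are unaffected. Each cohort contains two matched pairs, so early timing need not favor either arm if both members of a pair are interviewed together. The correction should still be made beforehand, since an interview held early cannot recover the months that follow it.

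**What to change.** In Section 9, Qualitative Analysis, replace months 26-30 with months 30-33. State that each organization is interviewed at its own cohort's month 18, alongside the end-of-intervention surveys. While editing, settle whether the earliest end is month 29 (training at month 11 plus 18) or month 30.

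For round 2, define when the sustainability phase starts and ends for each cohort. Reconcile the 6-month windows in Sections 3 and 5 with months 11-47 and 11-50 in Table 1 and the 36 months of access in Section 8. Then time round 2 to the resulting phase end, cohort by cohort. Do not move it to months 36-39 on the present text.

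The cost is a few lines of protocol text and some rescheduling, with the same interviews, sites and staff. The last round 1 interviews would fall up to 3 months later than now planned (month 33 instead of 30).
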